NON-INTERVENTIONAL STUDY (NIS) PROTOCOL

PASS information

ENCEPP/SDPP/13422

Title	Healthcare Professional and Patient Surveys to Assess the Effectiveness of Additional Risk Minimisation Measures for Concentrated Insulin Lispro (Humalog 200 units/ml KwikPen; Liprolog 200 units/ml KwikPen)
Protocol version identifier	Version 1.0
Date of last version of protocol	30 November 2015
EU Post Authorisation Study (PAS) register number	
Active substance	Drugs Used in Diabetes, Insulin Lispro ATC code: A10AB04
Medicinal product	Humalog 200 units/ml KwikPen Liprolog 200 units/ml KwikPen (in Germany only) (For purposes of this protocol, the term Humalog 200 units/ml KwikPen will refer to both trade names Humalog and Liprolog)
Product reference	EU/1/96/007/039-042 EU/1/01/195/028-29
Procedure number	EMEA/H/C/000088/MEA/025
Marketing Authorisation Holder (MAH)	Eli Lilly Nederland B.V.
Joint PASS	No

**Non-Interventional Study Protocol
for Humalog 200 units/ml KwikPen
Version 1.0**

Research question and objectives	This study aims to evaluate the impact of the additional risk minimisation measures on healthcare professional and patient understanding and behaviour regarding the risk of hypoglycaemia and/or hyperglycaemia due to medication errors associated with administration of Humalog 200 units/ml KwikPen.
Country(-ies) of study	Germany, United Kingdom (UK, if product uptake does not allow for participation, another comparable EU country will be selected), and a 3 rd country to be determined based on launch and product uptake.
Author	[name], Pharmacoepidemiologist Eli Lilly and Company

Marketing Authorisation Holder(s)

Marketing Authorisation Holder(s)	Eli Lilly Nederland B.V. [name] The Netherlands
MAH contact person	[name], Pharmacoepidemiologist Eli Lilly and Company

1. Table of Contents

Section	Page
1. Table of Contents.....	4
2. List of abbreviations.....	8
3. Responsible parties	10
4. Abstract	11
4.1. Rationale and Background.....	11
4.2. Research Questions and Objectives	12
4.3. Study Design.....	12
4.4. Populations	13
4.5. Study Endpoints	13
4.6. Variables.....	14
4.7. Data Sources	14
4.8. Study Size	14
4.9. Data Analysis.....	14
4.10. Milestones.....	14
5. Amendments and updates.....	16
6. Milestones.....	17
7. Rationale and background	18
8. Research question and objectives	20
9. Research methods	22
9.1. Study design.....	22
9.2. Setting.....	23
9.2.1. Inclusion criteria	24
9.2.2. Exclusion criteria	25
9.3. Variables.....	25

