9.2. Setting

The assessment surveys will be executed as soon as 12 months but no later than 18 months from launch of the product in Germany, the UK (if product uptake does not allow for participation, another comparable EU country will be selected), and a third EU country to be determined. Countries will be selected based on a sufficient number of prescribers and volume of prescriptions to allow for a successful enrolment of HCPs and patients. Pan-European diabetes treatment guidelines issued by professional organizations such as European Association for the Study of Diabetes (EASD; Inzucchi et al. 2015) and the European Society of Cardiology for the management of patients with diabetes, such that the difference in clinical practices in different EU countries should be negligible (ESC Task Force 2013). Therefore, selection bias will be largely prevented due to common clinical practice, standardized messaging, and survey implementation. The timing of the initiation of the survey depends on the product launch dates and the product uptake in each country.

The target population in each selected county will receive the same risk communication, to be provided in their official national language. Additionally, the same survey will be used in all 3 countries in order to test the target population on the same key safety messages. As such, variability of survey results based on geography is not anticipated and therefore 3 countries will be representative of the EU.

The UBC will administer the surveys to the study populations who respond to the invitations to participate in the study. Every effort will be made to ensure the samples participating from each country in the survey will be proportional to the expected eligible population among participating countries. The EDC system will be programmed to ensure desired distribution by requiring a minimum number of eligible participants from each country.

HCPs:

Surveys targeting eligible HCPs will be administered via the Internet, which will allow respondents to participate at a time and location that is convenient for them, and by telephone, to allow participation of respondents who do not have Internet access. Both modalities will offer the same survey.

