Notices will be sent and telephone calls will be made periodically to HCPs reminding them to invite patients to participate in the survey. During reminder telephone calls, feedback will be elicited regarding barriers to patient participation. If feedback is received showing that Internet and telephone modalities are barriers to survey completion, HCPs will be provided with paper versions of the survey. Each paper survey will include a postage paid envelope for returning the completed patient survey.

Patients who complete the survey will be offered reimbursement for their time spent participating as governed by local laws and country regulations.

If the rate of response is not sufficient to reach the goal population within the planned survey period, Lilly may employ additional measures in an effort to complete the sample, such as but not limited to, extend the survey period, increase the payment amount provided to stakeholders as allowed by local laws and country regulations, increase the frequency of or change the method of outreach to HCPs, and allow for respondents to schedule an appointment to take the survey over the phone or provide the means to participate by paper survey.

To ensure comprehension of the invitations and surveys, all of the outreach will be conducted in the official national language. The survey and invitation as well as any reminder letters will be translated by a certified translation vendor.

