9.2.1. Inclusion criteria

The HCPs must meet the following criteria to be eligible for inclusion in the survey:

- HCPs are aware of the insulin product Humalog 200 units/ml KwikPen; and
- HCPs are involved in the treatment and management of patients with diabetes.

Patients must meet all of the following criteria to be eligible for inclusion in the survey:

- Patients are 18 years or older;
- Patients have diabetes; and
- Patients have been prescribed Humalog 200 units/ml KwikPen.

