9.4. Data sources

In this survey, data sources for HCPs may be Lilly's lists of HCPs who received the DHPC (in countries where local privacy regulations or standard practices allow this list to be provided to UBC) and/or UBC's HCP reference files or panels. From these data sources, random samples of HCPs will be invited to participate in the survey and to invite patients to participate in the survey.

Structured, self-administered surveys (Appendix I.1 and Appendix I.3) comprised of closed-ended questions or statements with multiple response choices (that is, questions or statements asking the respondents to choose from a defined list of responses) will be used to collect the survey data. The surveys will collect data on respondent characteristics and their responses to

the risk understanding questions. The data collected from the surveys will be used to inform the evaluation of the effectiveness of the risk minimisation measures.

The survey is designed to be completely voluntary and anonymous to prevent the collection of any personal identifying information from participants. Each participant will be given a unique code to access the survey. Each code is deactivated upon its use to prevent the code from being used to complete the survey twice. Each code is randomly assigned and not tracked; therefore, no identification of patients who have or have not responded can be performed. The participants do not have to actively ‘decline to complete the survey’. Therefore, there is no ability to track which participants are actively deciding to not complete the survey. This survey design encourages patient participation and answer honesty by ensuring that the responses are completely anonymous.

Each survey will begin with a screening module with questions to confirm eligibility. Depending on the answers to the screening questions, survey participation will either be terminated or continued. If ineligible, the respondent is immediately notified with a “thank you” message that survey participation has ended. If eligible, the respondent is allowed to continue survey participation.

HCPs:

Screening questions:

- Agreement to participate
- Involved in the management of patients with diabetes
- Prior or current employment by Lilly, UBC, or any national medical governing body, such as but not limited to EMA, MHRA, and BfArM
- Awareness of Humalog 200 units/ml KwikPen

Data on demographic characteristics:

- Age
- Sex
- Role at facility
- Facility type
- Country

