This survey should take approximately 15 minutes to complete. If you cannot complete the survey at this time, please return when you can. Once you begin the survey you will need to answer all questions; you will not be able to access the survey again if you exit.

Thank you in advance for your participation. Please note the application will time out after 30 minutes of inactivity.

If you are ready to begin the survey at this time, please click continue. If not, click Return Later.

Please note: Do not use the browser's back button during this survey.

[END WELCOME PAGE]

[BEGIN SCREENING QUESTIONS]

Please provide a response to all questions and statements.

1. Do you agree to take part in this survey about Humalog[®] 200 units/ml KwikPen[™]?
 - Yes
 - No **[TERMINATE]**

2. Have you been diagnosed with diabetes?
 - Yes
 - No **[GO TO Q9; TERMINATE AFTER Q12]**
 - I don't know **[GO TO Q9; TERMINATE AFTER Q12]**

3. How long have you had diabetes?
 - Less than 1 year
 - 1 – 5 years
 - 6 – 10 years
 - 11 – 15 years
 - More than 15 years
 - I don't know
 - I don't have diabetes**[GO TO Q9; TERMINATE AFTER Q12]**

4. Do you use injectable insulin to treat your diabetes?
 - Yes
 - No **[GO TO Q6; TERMINATE AFTER Q12]**
 - I don't know **[TERMINATE AFTER Q12]**
 - I don't have diabetes **[TERMINATE AFTER Q12]**

5. For how long have you been using injectable insulin to manage your diabetes?
- Less than 1 year
 - 1 – 5 years
 - 6 – 10 years
 - 11 – 15 years
 - More than 15 years
 - I don't know
 - I don't have diabetes/I don't use insulin **[GO TO Q9; TERMINATE AFTER Q12]**
6. Have you been prescribed Humalog 200 units/ml KwikPen at least once?
- Yes
 - No **[GO TO Q8; TERMINATE AFTER Q12]**
 - I don't know **[GO TO Q8; TERMINATE AFTER Q12]**
 - I don't have diabetes/I don't use insulin **[GO TO Q8; TERMINATE AFTER Q12]**
7. For how long have you been using Humalog 200 units/ml KwikPen?
- I have not used it yet
 - Less than 3 months
 - 3 – 6 months
 - 7 – 12 months
 - More than 1 year
 - I don't know

- I don't have diabetes/I don't use Humalog 200 units/ml KwikPen **[GO TO Q9; TERMINATE AFTER Q12]**
8. What type of insulin did you use prior to using Humalog 200 units/ml KwikPen?
- Humalog 100U/ml
 - Other 100U/ml insulin
 - I don't know/I don't remember
 - I don't have diabetes/I don't use Humalog 200 units/ml KwikPen **[TERMINATE AFTER Q12]**
9. What is your gender?
- Male
 - Female
10. What is the highest level of education you have completed?

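### The draft patient survey names only Humalog, so German patients prescribed Liprolog, who count as eligible, may be screened out at Q6 or answer uncertainly because of the brand name

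*Protocol*

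**What the plan says.** The title page lists two trade names, the second being "Liprolog 200 units/ml KwikPen (in Germany only". For the Protocol's own purposes, "the term Humalog 200 units/ml KwikPen will refer to both trade names Humalog and Liprolog". The countries are "Germany, United Kingdom (UK, if product uptake does not allow for participation, another comparable EU country will be selected", plus a third to be chosen, so Germany is fixed.

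Section 9.2.1 requires that "Patients have been prescribed Humalog 200 units/ml KwikPen". Read with the title-page definition, this admits Liprolog patients.

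In Appendix I.3, Q6 asks "Have you been prescribed Humalog 200 units/ml KwikPen at least once". No and I don't know both route to Q8 and terminate after Q12. Every other visible mention of the product (Q1, Q7, Q8, Preamble 2, Q14 to Q16) also says Humalog alone.

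On localisation, Section 9.2 says that "the same survey will be used in all 3 countries in order to test the target population on the same key safety messages", and that "The survey and invitation as well as any reminder letters will be translated by a certified translation vendor". Neither statement mentions trade names.

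**The concern.** A definition on a protocol's title page binds people who read the protocol. A survey respondent sees the survey. If the pen and prescription say Liprolog, a careful respondent could truthfully answer No to Q6, and the survey would then drop someone whom the inclusion criteria admit.

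Two things are at stake:

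- **Selection.** Part of the German target population could be lost because of its brand, although the study title covers both brands. Section 9.2 rests its claim that three countries represent the EU on identical communication and an identical survey. In Germany the product label seen by patients may not match that survey.
- **Measurement.** For Liprolog patients who pass Q6, Q14 asks about switching between strengths of Humalog, and Q15 about a communication whose title carries only the Humalog name. Under Section 9.7, I don't know on a key-message question is generally scored incorrect, so an unfamiliar brand could be recorded as a failure to understand the risk.

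**Working it through.** The point turns on the text and skip logic. The plan states no figure for it.

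**1. Definition against instrument.** Title page plus Section 9.2.1: prescribed Humalog 200 or Liprolog 200 means eligible. Appendix I.3, Q6: prescribed Humalog 200 means continue; No or I don't know means terminate. The eligibility definition includes Liprolog patients and the wording of the eligibility question does not.

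**2. Is the gap closed by localisation?** The draft carries country-specific instructions for the website (Q15), for payment (Closing 1) and for the country list. It has none for the trade name. Country is asked at Q11, after Q6, so a display rule driven by that answer would come too late. The second name has to be in the German version itself.

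**3. Could the error be seen or undone later?** Respondents cannot go back (Sections 9.4.1 and 9.9.1). Access codes are deactivated on use and not tracked (Section 9.4). No item records the brand. A terminated respondent does give a country at Q11, so Q6 failures could be counted for Germany, but a Liprolog user could not be told apart from a true non-user. Under Section 9.7 both fall among ineligible patients.

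**4. Illustrative size.** Let L be the share of otherwise eligible German respondents who use Liprolog, and q the share of those who answer No or I don't know at Q6. Both are assumptions.

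Loss of eligible German respondents = L × q. Liprolog share among German completers = L(1 − q)/(1 − Lq).

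Example, L = 30%, q = 50%: loss = 0.30 × 0.50 = 15%; share among completers = 0.15/0.85 = 17.6%, instead of 30%.

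| L | q = 25%: lost; share left | q = 50%: lost; share left | q = 100%: lost; share left |
|---|---|---|---|
| 10% | 2.5%; 7.7% | 5%; 5.3% | 10%; 0% |
| 30% | 7.5%; 24.3% | 15%; 17.6% | 30%; 0% |
| 50% | 12.5%; 42.9% | 25%; 33.3% | 50%; 0% |

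The range is too wide to support a point figure.

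**5. Precision.** Equation 1 at a 50% response rate gives 1.96 × √(0.5 × 0.5/280) = 5.86%, which reproduces the 5.9% in Table 1. Section 9.4.1 closes data collection when the desired number of surveys is complete, so screened-out respondents are replaced. The sample stays at 280 and Table 1 stands. What changes is who is in the sample.

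**The case against.** The other side has several good points.

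- **Termination is not certain.** A reader might infer that German Liprolog patients will all be rejected. The documents do not show that. Under Section 9.2, patients are invited by the HCP who prescribed the product, and some will recognise it under the other name. Preamble 1 (mentioned in Section 10.1) and the patient invitation letter are not in the text available, and either could introduce Liprolog. This stands, and makes it a risk. It does not remove the point, because Q6 itself still names one brand.
- **The survey is a draft.** Annex 1 calls it so, and the communications await local approval, so the German title may differ. That is true, but the only localisation described is translation, and a translator has no instruction to add a trade name.
- **Prior insulin.** A reader might infer that Q8 misclassifies patients switched from Liprolog 100 U/ml. The Protocol mentions no such product, and a Liprolog user who accepted Humalog at Q6 might equally tick Humalog 100U/ml. Only a conditional remark survives.
- **HCP screener.** A reader might infer the same fault from the Section 9.4 entry "Awareness of Humalog 200 units/ml KwikPen". That line is protocol text, governed by the title-page convention, and HCP questions 1 to 15 are not visible. Only Q16 to Q20 can be seen to name Humalog alone.
- **A percentage of the whole sample.** Assuming Liprolog shares of 10% to 40% and a German share of one third to one half gives 0.10 × 1/3 = 3.3% up to 0.40 × 1/2 = 20%, but only if every Liprolog user fails Q6. If a quarter do, it is 0.8% to 5%. None of these inputs is in the Protocol.

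**Conclusion.** The point holds as a mismatch between the eligibility definition and the patient survey. Followed as written, the draft can screen out eligible German Liprolog patients and count them as ineligible, in a way that the collected data cannot reveal or correct. It can also depress Q14 scores and turn Q15 answers into I don't know for reasons of brand.

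The size is unknown. It depends on the Liprolog share in Germany and on how these patients would answer, and neither is given. The conclusion assumes that at least some Liprolog users answer Q6 literally and that no unseen text tells them that Humalog includes Liprolog.

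A reader might go further and infer that the German results are biased by a given amount, or that the study can say nothing about Liprolog. The first would need evidence that Liprolog and Humalog users differ in knowledge or in how they answer; the second would need nearly all Liprolog users to fail Q6. The documents show neither. The case for acting is that the error could not be detected afterwards and costs almost nothing to prevent.

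**What to change.** Before translation:

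1. In the German patient survey, show 'Humalog/Liprolog 200 units/ml KwikPen', or a country-specific brand placeholder, at Q1, Q6 to Q8, Preamble 2 and Q14 to Q16. Refer to the communication by its locally approved title.
2. Do the same in HCP questions Q16 to Q20. Check the HCP screener, Preamble 1 and both invitation letters for the same point.
3. In Section 9.2, replace the statement about one identical survey with 'the same survey with the locally marketed trade name(s)'.
4. If a same-substance 100 U/ml product is sold under the other name, have Q8 group it with Humalog 100 U/ml, so that the prior-insulin subgroups in Section 9.7 keep their meaning.

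Optionally, add one item recording the brand for German respondents, so that the report can show that both were reached.

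The cost is wording in draft documents, plus one item if the option is taken. No extra respondents or procedures are needed, and the sample size is unaffected.

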9.1. Study design

This study is a multi-national, observational, cross-sectional survey design. Separate surveys will be administered to HCPs involved in the treatment and management of patients with diabetes and to patients with diabetes who have been prescribed Humalog 200 units/ml KwikPen. The study has been designed and will be executed and analysed in collaboration with UBC. The surveys have been developed to enable the study objectives to be met (Section 8).

User Testing was performed on each survey with a sample of 10 HCPs and 9 patients. The User Testing procedure was designed to assess comprehension among patients regarding the words and phrases used in select survey questions and response options. User Testing also assessed the clarity of the survey questions as presented to HCPs and the interest and acceptance of the surveys among all prospective respondents, flow and ease of completing the surveys, and preferred modes of administration. Findings and recommendations from User Testing have been incorporated into the surveys.

Assessment of the additional risk minimisation measures in the participating samples will be used to determine whether the target populations are aware of and adherent to the key message themes regarding the risk of hypoglycaemia and/or hyperglycaemia attributed to medication errors or misuse associated with the administration of Humalog 200 units/ml KwikPen. All statistical analyses will be descriptive, that is, no formal hypothesis will be tested. Study endpoints are as follows:

The tools will be considered effective if the majority of respondents demonstrate they are aware of the key risks communicated.

HCPs:

- Demonstrating that they understand the key safety messages communicated in the DHPC
- Reporting that they provided the patient communication or means to access the communication to patients at the time of first Humalog 200 units/ml KwikPen prescription
- Reporting they discussed the key safety messages in the patient communication with their patients who are receiving their first prescription of Humalog 200 units/ml KwikPen

Patients:

- Demonstrating that they understand the key safety messages communicated
- Reporting that they were provided with a copy of or means to access the Humalog 200 units/ml KwikPen patient communication from their HCP at the time of initial prescription
- Reporting that they consider the key messages during administration of Humalog 200 units/ml KwikPen

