Eligible HCPs will receive an invitation letter via email if an email address is available, or a letter in the postal mail inviting them to participate in the survey. The invitation letter (Appendix I.2) will include: an overview of the rationale for the survey, information on how to access the survey online and by telephone, and a unique User Identification (ID) to ensure that the invitation is used only once.

HCPs in the applicable countries who are involved in the treatment and management of patients with diabetes will be invited to participate in the survey. The respondent population will include a mix of prescribers who have and have not prescribed Humalog 200 units/ml. The response rate will be monitored throughout the data collection period. Reminder notices will be sent via email and postal mail, and telephone calls will be made periodically to HCPs who have been invited

but not yet participated. The HCPs that complete the survey will be reimbursed for their time spent participating as governed by local laws and country regulations.

Patients:

Surveys targeting eligible patients will be administered via the Internet, which will allow respondents to participate at a time and location that is convenient for them, and by telephone, to allow participation of respondents who do not have Internet access or are not computer literate. Both modalities will offer the same survey.

Patients will be recruited via study packets that will be provided to HCPs due to privacy concerns in the EU. All HCPs who receive an invitation to participate in the HCP survey will also receive a study packet of patient invitations in the postal mail and a letter asking them to invite eligible patients to participate in the survey. The packet will contain 10 invitation letters to be distributed. The patient invitation letter (Appendix I.4) will include an overview of the rationale for the survey, information on how to access the survey online, the toll-free number for accessing the telephone survey, and a unique User ID to ensure that the invitation is used only once. The HCPs will not be asked to select specific patients based on eligibility criteria. HCPs will forward the patient invitations to their patients for whom they have prescribed Humalog 200 units/ml. In the event an HCP has prescribed Humalog 200 units/ml to more than 10 patients, the HCP will arbitrarily select 10 patients regardless of any additional eligibility criteria.

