9.7. Data analysis

Data collected from the survey will be reported as descriptive statistics. Frequency distributions with 95% CIs will be calculated for respondent responses to all questions that address the survey objectives. Responses to each question relating to the key risk messages will be categorised as “Correct response” and “Incorrect response”. “I don’t know” is generally categorised as an incorrect response unless otherwise specified.

In addition to the overall analysis, survey data will be analysed to determine if there are any differences by country and, for HCPs, medical speciality. Sub-group analyses will include all requested subgroups including patients switched from other 100 units/ml insulins, Humalog 100 U/ml, how long patients were on insulin, and which other insulins have been used as captured in the questionnaire. Additionally, a subgroup analysis will be performed to identify possible differences in the responses based on length of Humalog 200 units/ml use.

The following will be reported as part of the analysis:

HCPs:

- *Survey administration*
 - The number of survey invitations issued by strata (i.e., by country and specialty)
 - The number of survey invitations returned due to incorrect mailing address of HCPs invited to participate in the survey
 - The number of HCPs who responded to the invitation to participate in the survey
 - The number of HCPs eligible for participation in the survey
 - The number of ineligible HCPs along with the reasons for ineligibility
 - The number of eligible HCPs who completed the survey
- *Demographic characteristics of participants*
 - Distribution of participants by age groups
 - Distribution of participants by sex
 - Distribution of participants by practice setting
 - Distribution of participants by country
 - Distribution of participants by medical specialty
 - Distribution of participants by years in medical practice
 - Distribution of participants by number of patients treated with Humalog 200 units/ml KwikPen
- *Responses to questions pertaining to the survey objectives:*
 - Awareness of the DHPC on the correct use of Humalog (insulin lispro) 200 units/ml KwikPen
 - Understanding of the risk messages
 - Self-reported practices with respect to communication of the key risk messages in clinical practice

Patients:

- *Survey administration*
 - The number of HCPs asked to invite patients to participate
 - The number of invitations provided to HCPs

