APPENDIX I.3 PATIENT SURVEY

SURVEY LEGEND

- **[PROGRAMMER]** is used to indicate directions to the programmer and is set in bold, red, uppercase letters between square brackets.
- **(INTERVIEWER)** is used to indicate directions to the phone interviewer and is set in bold, blue, text between parentheses. This text appears when content is to be administered by phone only (for example, spontaneous safety event reporting).
- **[ONLINE]** indicates a question/section is worded specifically for administering the survey online.
- **[TELEPHONE]** indicates a question/section is worded specifically for administering the survey over the telephone.
- **[BEGIN SURVEY CONTENT]** and **[END SURVEY CONTENT]** are used to indicate to the programmer the type of survey administration and the beginning and end of the survey or sections within the survey content.
- **[TERMINATE]** is displayed next to responses that should cause the survey to end. The following termination language will be programmed into the survey or read by the interviewer.

Thank you very much for your time today. Based on your answer, you are not eligible to take this survey. We appreciate your interest in the survey.

- **[RANDOMISE LIST]** is inserted before questions to indicate to the programmer that the responses should be randomised. Responses such as “I don’t know,” “Prefer not to answer” or “None of the above” will always appear at the end of the randomised responses.
- **[GO TO Qx]** (skip logic) is inserted after a response to indicate to the programmer that the survey should skip to the indicated question (for example, **[GO TO Q17]** skips to question 17). If no skip logic is indicated the survey continues to the next question in the sequence.

SURVEY LEGEND

- **[MULTILINE INPUT]** indicates to the programmer that multiple lines should be provided for data entry.
- **[FREE TEXT]** indicates to the programmer that one line should be provided for data entry.
- **[DROP-DOWN LIST INPUT WITH COUNTRIES TABLE]** indicates to the programmer that the response should be a drop-down list containing the countries in the table below.

United Kingdom
(or other comparable EU
country based on product
uptake)

Germany

TBD

The following is used to categorise survey populations into standard geographic regions but it is not displayed in the survey.

[WELCOME PAGE]

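### Patient screening question 6 stops invited patients who are unsure whether they were prescribed the 200 units/ml pen, so probably eligible respondents leave the understanding denominator; question 4 is also stricter than section 9.2.1

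*Protocol*

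**What the plan says.** **Eligibility.** Protocol section 9.2.1 sets three patient criteria: adult age, diabetes, and "Patients have been prescribed Humalog 200 units/ml KwikPen". Awareness of the product is a criterion for HCPs in the same section, but not for patients.

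**Recruitment.** Section 9.2 (Patients) states that "HCPs will forward the patient invitations to their patients for whom they have prescribed Humalog 200 units/ml".

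**Screening.** In Appendix I.3, question 6 reads "Have you been prescribed Humalog 200 units/ml KwikPen at least once". Its don't-know option carries the instruction "I don't know [GO TO Q8; TERMINATE AFTER Q12". Question 4 (current use of injectable insulin) routes a no answer to question 6 but still terminates after question 12; its don't-know option is "I don't know [TERMINATE AFTER Q12". A terminated respondent is told: "Based on your answer, you are not eligible to take this survey". Questions 14 (key messages) and 15 (receipt and use of the communication) come later and are never shown.

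**Analysis.** Section 10.2 restricts the analysis to complete surveys. Section 9.7 says that a don't-know answer to a key-message question "is generally categorised as an incorrect response unless otherwise specified". It also plans a count of ineligible patients with reasons. The success statement in section 9.1 is "The tools will be considered effective if the majority of respondents demonstrate they are aware of the key risks communicated".

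**The concern.** Anyone reached by the planned route should already hold a prescription for the pen. An invited patient who is unsure at question 6 may well be a true recipient who cannot identify the product. The study concerns medication errors with this product, and one of the two patient key messages is about changing between strengths, so such a patient belongs to the population of interest. The screener classes that patient as ineligible before understanding is measured.

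Selection would then act on a variable that is plausibly related to the outcome. If those removed are less well informed, each patient understanding proportion is too high, in the direction that favours the majority criterion. Recruiting to 280 completed surveys does not dilute this, because stopped respondents do not count towards the 280. The limitations in section 9.9 cover self-selection, compliant HCPs, recall and self-report, but not this screen.

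Question 4 raises a separate matter of consistency: it adds a condition (current insulin use) that section 9.2.1 does not contain.

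**Working it through.** **1. The plan's own precision.** Equation 1 in section 9.5 gives a half-width of 1.96·√[p(1−p)/280]. At p = 0.80 this is 1.96·√(0.16/280) = 4.69 points; Table 1 shows 4.7. The other rows also reproduce: 5.86, 5.74, 5.37 and 3.51 points at 50%, 60%, 70% and 90%, against 5.9, 5.7, 5.4 and 3.5.

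**2. Inputs for the size of the effect.**
- p: proportion correct among completers (illustrative; Table 1 uses 50% to 90%).
- f: share of otherwise eligible responders stopped by a don't-know at question 6. Not in the protocol; assumed 5% or 10%.
- q: proportion of those stopped who would have answered correctly. Not in the protocol; assumed 0% to 50%.

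**3. Formula.** Rate with the stopped respondents restored = (1−f)p + fq. Overstatement = p − [(1−f)p + fq] = f(p−q). It is positive only if q < p.

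**4. Results.** The number stopped alongside 280 completers is 280·f/(1−f): about 15 at f = 5% and about 31 at f = 10%.

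| Observed p | f | Restored rate, q = 0 | Restored rate, q = 50% | Overstatement (points) |
|---|---|---|---|---|
| 80% | 5% | 0.95·80 = 76.0% | 76.0 + 0.05·50 = 78.5% | 4.0 to 1.5 |
| 80% | 10% | 0.90·80 = 72.0% | 72.0 + 0.10·50 = 77.0% | 8.0 to 3.0 |
| 55% | 10% | 0.90·55 = 49.5% | 49.5 + 0.10·50 = 54.5% | 5.5 to 0.5 |

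**5. Against the half-width.** At an observed 80%, the overstatement equals the 4.69-point half-width when f = 4.69/80 = 5.9% (q = 0), or when f = 4.69/(80−50) = 15.6% (q = 50%).

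**6. Against the majority line.** An observed 55% falls to 50% at f = 1 − 50/55 = 9.1% if q = 0. At q = 50% the restored rate stays above 50% for any f below 100%.

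**7. Question 4 beside section 9.2.1.** Take an adult with diabetes who was prescribed the pen and is not currently injecting insulin. Section 9.2.1 admits this patient. In Appendix I.3 the patient answers no at question 4, goes to question 6, answers yes, and is still terminated after question 12. The two texts give different answers for the same person.

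**The case against.** **The invitation does not prove a prescription.** This stands. Every invited HCP receives ten letters, and those HCPs include some who have not prescribed the product (section 9.2). Access codes are randomly assigned and untracked (section 9.4), so no respondent can be tied to a prescribing record. Question 6 is the only respondent-level check on that criterion, and ending on an unconfirmed criterion is ordinary screening. The recruitment route makes eligibility probable, not certain. That supports flagging these respondents rather than counting them without comment.

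**A reader might infer that section 9.7 is contradicted**, because it scores don't-know as incorrect while question 6 removes it. It is not. The scoring rule applies to questions on the key risk messages, and recalling which product was prescribed is not one of them.

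**A reader might infer that those stopped are confused about insulin strength.** The documents do not show this. Question 1 already names the product, and a don't-know could equally reflect a mis-forwarded letter or an unfamiliar name; the product is sold as Liprolog in Germany.

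**A reader might take question 7's option of not having used the pen yet as proof that question 4 is wrong.** It is not proof: a patient on another insulin who has not started this pen passes question 4 and can choose that option consistently. The conflict is with section 9.2.1.

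**Part of this is already covered.** Section 9.7 reports reasons for ineligibility, and a sensitivity analysis may sit in an SAP that is not shown. This stands for the analysis. But the count gives a bound only if don't-know at question 6 is tabulated separately, and no analysis plan can supply answers to items that were never asked.

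**Conclusion.** The point holds in a limited form. The routing is explicit: a don't-know at question 6 removes an invited, probably eligible patient before understanding is measured, although section 9.2.1 asks only that the product was prescribed. Upward bias is an inference that requires q < p. Its size, f(p−q), cannot be fixed from the protocol. On the assumed ranges, an observed 80% is overstated by 1.5 to 4.0 points at f = 5% and by 3.0 to 8.0 points at f = 10%. It may therefore lie well inside the 4.7-point half-width. A reader might infer that the majority conclusion is at risk, but that needs an observed rate near 50%, a sizeable f and a low q together, and nothing in the protocol points to that combination.

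The mismatch between question 4 and section 9.2.1 is textual and needs no assumption.

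**What to change.** - **Question 6.** Let a don't-know answer continue to questions 14 and 15 with a flag. Report the patient understanding endpoints with and without flagged respondents.
- **If termination is kept.** Tabulate don't-know at question 6 as its own reason among the ineligible patients, separately from no. Give a bound that adds these respondents to the denominator as incorrect, that is p(1−f).
- **Question 4.** Reconcile its routing with section 9.2.1: either do not end the survey for a patient who reports a prescription at question 6, or state current insulin use as an inclusion criterion.

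The cost is a change to skip logic in surveys that Annex 1 still lists as drafts, plus one extra table. The downside is that a few people with mis-forwarded invitations may enter; the flag isolates them. The routing needs to be settled before the survey opens.
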